 1.2 Synopsis, 6.1.1 Dosing and Duration of Treatment, 6.1.3.1 Drug-drug Interactions, 6.5.4 Acalabrutinib Drug-drug Interaction Guidance in the Presence of Life- threatening COVID-19 Infection, 6.5.4.2 Active Substances That May Decrease Acalabrutinib Plasma Concentrations 	For subjects not on PPIs, removed volume (240 mL) of water and just stated that it should be taken with water. For subjects who are on PPIs, changed volume of COCA- COLA from 240 mL to "at least 100 mL".	Based on in-vitro data, administering acalabrutinib 100 mg oral capsules (in the presence of PPIs) with at least a 100 mL of COCA-COLA is considered to be adequate for mitigating the effect of PPIs on acalabrutinib PK/PD	Non-substantial
1.2 Synopsis,4.4 Internal DMC	Added text to indicate that the iDMC will review safety and efficacy data. In addition, the iDMC may support any health authority interactions or internal discussions based on their review, and the study team will remain blinded to the data that the iDMC will review.	For transparency and to preserve the trial integrity	Substantial
5.2 Exclusion Criteria	Removed the cutoffs for oxygen flow rates from Exclusion Criterion 1 and indicated that subjects should be considered for eligibility in part based on their ability to swallow pills	Clarified which patients with respiratory failure are eligible for enrollment	Substantial

Section number and name	Description of change	Brief rationale	Substantial/ non-substantial
	Added an exception to Exclusion Criterion 8 to indicate that AST and/or ALT can be up to $5 \times$ ULN if considered due to underlying COVID-19, but cannot be associated with concurrent elevated bilirubin (up to $2 \times$ ULN)	Hepatotoxicity and ALT/AST are not currently adverse drug reactions for acalabrutinib and there is evidence for ALT/AST increases associated with COVID-19 (Cai et al 2020, Guan et al 2020)	Substantial
8.1 ScreeningAssessments,8.1.1 Informed Consent	Moved second paragraph under Section 8.1.1 to Section 8.1	Paragraph relates to all screening visits	Non-substantial
9.6. Statistical Analyses	Added a description of the timing of the primary analysis of the study and the updated analysis	For clarity	Non-substantial

1.1 Schedule of Activities (SoA)

The SoAs for Arm 1 (acalabrutinib + best supportive care [BSC]) and Arm 2 (BSC only) are presented in Table 1 and Table 2, respectively.

Table 1Schedule of Activities - Arm 1 (Acalabrutinib + BSC)

Assessments	Screening (Day -3 to Day -1 ¹)	Daily until hospital discharge	Day 10 or discharge ^h	Day 14 (±2 days) after randomi- zation	Day 28 (±3 days) after randomi- zation	Safety FU 28 (±3) days after last dose of acala- brutinib ⁱ	Long-term FU 90 (±7) days after randomi- zation ^{i,j}	CSP section
Informed consent	X							8.1.1
Demography	Х							8.1.2
Determine eligibility	Х							5.1, 5.2
Medical history and COVID-19 epidemiology	Х							8.1.4
Physical examination (symptom driven, including lung auscultation, height, weight)	Х							8.1.5
Chest imaging	X r	As clinically indicated						8.1.5, 8.3
Electrocardiogram	X 1	As clinically indicated	Х					8.1.5, 8.3
Echocardiogram	As clinically indicated	As clinically indicated						8.1.5, 8.3
Vital signs (blood pressure, respiratory rate, oximetry, pulse and body temperature)	X ^s	Х	x	Х	X			8.1.6, 8.3
Local laboratory assessments:								
Urine or serum pregnancy test (for WOCBP only)	Х			Х		Х		8.1.7, 8.3
Hematology ^b	Х	Х	Х	Х	Х	X		8.1.8, 8.3
Serum or plasma chemistry ^c	Х	Х	Х	Х	Х	Х		8.1.8, 8.3
Arterial blood gases (if available) ⁿ	Х	Х		Х	Х			8.1.6, 8.1.8, 8.3, 8.4.1
Hepatitis B and C testing ^d	Х	As clinically indicated				As clinically indicated		6.6.3, 8.1.8, 8.3
Serum ferritin ^m	Х	qod (starting from Day 1)	Х	Х	Х			8.1.8, 8.3
Fibrinogen ^m	Х	qod						8.1.8, 8.3
PT, aPTT, and INR ^m	X	qod						8.1.8, 8.3

Table 1	Schedule of Activities - Arm 1 (Acalabrutinib + BSC)
---------	--

Assessments	Screening (Day -3 to Day -1 ¹)	Daily until hospital discharge	Day 10 or discharge ^h	Day 14 (±2 days) after randomi- zation	Day 28 (±3 days) after randomi- zation	Safety FU 28 (±3) days after last dose of acala- brutinib ⁱ	Long-term FU 90 (±7) days after randomi- zation ^{i,j}	CSP section
D-dimer ^m	Х	qod		Х	Х			8.1.8, 8.3
CRP	Х	Х	Х	Х	Х			8.1.8, 8.3
Procalcitonin (if available) ^m	Х	qod		Х	Х			8.1.8, 8.3
Cardiac troponin I ^m	Х	Day 5	Х					8.1.8, 8.3
SARS-CoV-2 RT-PCR virus testing for eligibility ^e	Within 7 days prior to randomi- zation							8.1.8, 5.1
Clinical assessments		As appl	icable until hos	pital discharge	•			8.4
9-point ordinal scale	Х	Х		Х	Х			8.8.1
Central laboratory assessments ^q								
Correlative samples ^{a,o}		Days 1 ^a , 3, and 7	Х	Х	Х		-	8.3
Immunophenotyping ^{a,g}		Days 1 ^a , 3, and 7	Х	Х	Х			8.3
Serum and nasal swab samples for SARS-CoV-2 viral load/viral shedding ^a		Days 1 ^a , 3, and 7	Х	Х	Х			8.3
201								
Acalabrutinib PK ^{p,t}		0.5 and 2 hours postdose on Day 3; 1 and 4 hours postdose on Day 7						8.3

Table 1Schedule of Activities - Arm 1 (Acalabrutinib + BSC)

Assessments	Screening (Day -3 to Day -1 ¹)	Daily until hospital discharge	Day 10 or discharge ^h	Day 14 (±2 days) after randomi- zation	Day 28 (±3 days) after randomi- zation	Safety FU 28 (±3) days after last dose of acala- brutinib ⁱ	Long-term FU 90 (±7) days after randomi- zation ^{i,j}	CSP section
Acalabrutinib administration		The first dose of acalabrutinib should be administered within 6 hours of randomization 100 mg bid (q12h) × 10 days (maximum)						6.1
Adverse events	X^k	Х	Х	Х	Х	X ^j		8.6
Concomitant medications	Х	Х	Х	Х	Х	X ^j		8.2
Survival status				Х	X	X ^j	Xj	4.5

anti-HBc = hepatitis B core antibody; aPTT = activated partial thromboplastin time, bid = twice daily; BSC = best supportive care; CD = cluster of differentiation; CRP = C-reactive protein; CT = computed tomography; ECG = electrocardiogram; FU = follow-up; COVID-19 = coronavirus disease 2019; CSP = Clinical Study Protocol; HBsAg = hepatitis B surface antigen; HCV = hepatitis C virus; ICF = Informed Consent Form; ICU = intensive care unit; INR = international normalized ratio; PBMC = peripheral blood mononuclear cell; PD = pharmacodynamics; PK = pharmacokinetics; PT = prothrombin time; q12h = every 12 hours; qod = every other day; RT-PCR = reverse transcriptase-polymerase chain reaction; SAE = serious adverse event; SARS-CoV-2 = severe acute respiratory syndrome coronavirus 2; WOCBP = women of childbearing potential.

^a Predose.

^b Hematology: complete blood count with differential includes, but not limited to white blood cell count, hemoglobin, platelet count, absolute neutrophil count (ANC) or percentage, red blood cell count, absolute monocyte count or percentage, and absolute lymphocyte count (ALC) or percentage.

- ^c Serum or plasma chemistry: albumin, alkaline phosphatase, alanine transaminase (ALT), aspartate aminotransferase (AST), bicarbonate, blood urea nitrogen (BUN), calcium, chloride, creatinine, glucose, lactate dehydrogenase (LDH), magnesium, phosphate/phosphorus, potassium, sodium, total bilirubin (direct and indirect bilirubin, if available), total protein and uric acid.
- ^d Hepatitis serology must include, at a minimum, HBsAg, anti-HBc, and HCV antibody. If additional hepatitis serology is collected per institutional guidelines, it should be recorded in the database. Additional testing information is provided in Section 6.6.3 and Section 8.1.8.
- e COVID-19 infection must be confirmed according to the World Health Organization criteria (including positive nucleic acid test of any specimen [eg, respiratory, blood, urine, stool, or other bodily fluid]) within 7 days prior to randomization. If test has already been documented within 7 days prior to randomization, no need to repeat the testing again.

f

- ^g Flow cytometry testing of peripheral blood will include, but is not limited to, CD3+, CD4+, CD8+, CD14+, CD19+, and CD16+/56+ cells.
- ^h If a subject is discharged prior to Day 7, he/she needs to visit the site for an assessment 2 to 4 days after discharge. Assessments should match those for Day 10.
- ⁱ Telemedicine is recommended for capturing adverse events concomitant medications, and survival. Safety laboratory tests can be done at the hospital or a local laboratory provided the results are ultimately captured in the clinical database for the study.
- ^j All subjects will be followed for survival for 90 (\pm 7) days.

Table 1Schedule of Activities - Arm 1 (Acalabrutinib + BSC)

	Screening (Day -3 to Day -1 ¹)	Daily until hospital discharge	Day 10 or discharge ^h	Day 14 (±2 days) after randomi- zation	Day 28 (±3 days) after randomi- zation	Safety FU 28 (±3) days after last dose of acala- brutinib ⁱ	Long-term FU 90 (±7) days after randomi- zation ^{i,j}	CSP section
--	--	-----------------------------------	-------------------------------------	--	--	--	--	----------------

^k After signing the ICF, but prior to randomization, only SAEs should be reported (see Section 8.6.2).

¹ Screening can be performed within 1 to 3 days prior to dosing, depending on the local requirements for laboratory turn-around times; ECG can be collected at any time during this screening window.

^m Serum ferritin, fibrinogen, PT, aPTT, INR, D-dimer, procalcitonin, and cardiac troponin I should be performed more frequently if clinically indicated.

ⁿ Arterial gases should be collected from subjects if the sample is easily accessible and the procedure will not be painful to subjects (ie, subject is in ICU or has arterial port). All available data from the arterial gases should be entered into the database. If the collection of arterial gases is not clinically indicated, the test should not be performed.

0

^p All blood samples for PK assessment (ie, 0.5, 1, 2, and 4 hours postdose) can also be collected during a single visit on Day 3 or after.

^q For all central laboratory assessments, sample collection windows of ± 1 day will be allowed for each of Days 3 and 7.

^r Per standard of care, chest imaging can be done by chest x-ray or CT scan with contrast, or any other appropriate means to confirm pneumonia prior to or upon hospitalization (within 7 days of randomization).

^s During screening, vital signs should be collected as close as possible to randomization on Day 1. If more than one value is obtained for vital signs during screening, the value closest to randomization should be used.

^t PK assessments will be conducted in up to 15 evaluable subjects and PD assessments in up to 15 evaluable subjects randomized to Arm 1 (acalabrutinib + BSC).

Table 2Schedule of Activities - Arm 2 (BSC Only)

Assessments	Screening (Day -3 to Day -1 ¹)	Daily until hospital discharge	Day 10 or discharge ^h	Day 14 (±2 days) after randomi- zation	Day 28 (±3 days) after randomi- zation	Safety FU 38 (±3) days after randomi- zation ⁱ	Long-term FU 90 (±7) days after randomi- zation ^{i,j}	CSP section
Informed consent	Х							8.1.1
Demography	Х							8.1.2
Determine eligibility	Х							5.1, 5.2
Medical history and COVID-19 epidemiology	Х							8.1.4
Physical examination (symptom driven, including lung auscultation, height, weight)	Х							8.1.5
Chest imaging	X q	As clinically indicated						8.1.5, 8.3
Electrocardiogram	X ¹	As clinically indicated	Х					8.1.5, 8.3
Echocardiogram	As clinically indicated	As clinically indicated						8.1.5, 8.3
Vital signs (blood pressure, respiratory rate, oximetry, pulse and body temperature)	X ^r	Х	Х	Х	Х			8.1.6, 8.3
Local laboratory assessments:								
Urine or serum pregnancy test (for WOCBP only)	Х			Х		Х		8.1.7, 8.3
Hematology ^b	Х	Х	Х	Х	Х	X		8.1.8, 8.3
Serum or plasma chemistry ^c	Х	Х	Х	Х	Х	X		8.1.8, 8.3
Arterial blood gases (if available) ⁿ	Х	Х		Х	Х			8.1.6, 8.1.8, 8.3, 8.4.1
Hepatitis B and C testing ^d	Х	As clinically indicated				As clinically indicated		6.6.3, 8.1.8, 8.3
Serum ferritin ^m	Х	qod (starting from Day 1)	Х	Х	Х			8.1.8, 8.3
Fibrinogen ^m	Х	qod						8.1.8, 8.3

Assessments	Screening (Day -3 to Day -1 ¹)	Daily until hospital discharge	Day 10 or discharge ^h	Day 14 (±2 days) after randomi- zation	Day 28 (±3 days) after randomi- zation	Safety FU 38 (±3) days after randomi- zation ⁱ	Long-term FU 90 (±7) days after randomi- zation ^{i,j}	CSP section
PT, aPTT, and INR ^m	Х	qod						8.1.8, 8.3
D-dimer ^m	Х	qod		Х	Х			8.1.8, 8.3
CRP	Х	Х	Х	Х	Х			8.1.8, 8.3
Procalcitonin (if available) ^m	Х	qod		Х	Х			8.1.8, 8.3
Cardiac troponin I ^m	Х	Day 5	Х					8.1.8, 8.3
SARS-CoV-2 RT-PCR virus testing for eligibility ^e	Within 7 days prior to randomi- zation							8.1.8, 5.1
Clinical assessments		As app	licable until ho	ospital discharge	2			8.4
9-point ordinal scale	Х	Х		Х	Х			8.8.1
Central laboratory assessments ^p								
Correlative samples ^{a,o}		Days 1 ^a , 3, and 7	Х	Х	Х		-	8.3
Immunophenotyping ^{a,g}		Days 1 ^a , 3, and 7	Х	Х	Х			8.3
Serum and nasal swab samples for SARS-CoV-2 viral load/viral shedding ^a		Days 1 ^a , 3, and 7	Х	Х	Х			8.3
CCI								
Adverse events	X ^k	Х	Х	Х	Х	Xj		8.6
Concomitant medications	Х	Х	Х	Х	Х	Xj		8.2
Survival status				Х	Х	Xj	Xj	4.5

Table 2Schedule of Activities - Arm 2 (BSC Only)

anti-HBc = hepatitis B core antibody; aPTT = activated partial thromboplastin time, BSC = best supportive care; CD = cluster of differentiation; CT = computed tomography; ECG = electrocardiogram; FU = follow-up; COVID-19 = coronavirus disease 2019; CRP = C-reactive protein; CSP = Clinical Study Protocol; HBsAg = hepatitis B surface antigen; HCV = hepatitis C virus; ICF = Informed Consent Form; ICU = intensive care unit; INR = international normalized ratio; PBMC = peripheral blood mononuclear cell; PT = prothrombin time; qod = every other day; RT-PCR = reverse transcriptase-polymerase chain reaction; SAE = serious adverse event; SARS-CoV-2 = severe acute respiratory syndrome coronavirus 2; WOCBP = women of childbearing potential.

^a Predose.

Table 2Schedule of Activities - Arm 2 (BSC Only)

	Assessments	Screening (Day -3 to Day -1 ¹)	Daily until hospital discharge	Day 10 or discharge ^h	Day 14 (±2 days) after randomi- zation	Day 28 (±3 days) after randomi- zation	Safety FU 38 (±3) days after randomi- zation ⁱ	Long-term FU 90 (±7) days after randomi- zation ^{i,j}	CSP section	
b	Hematology: complete blood count with differential includes, but not limited to white blood cell count, hemoglobin, platelet count, absolute neutrophil count (ANC) or percentage, red blood cell count, absolute monocyte count or percentage, and absolute lymphocyte count (ALC) or percentage.									
c	Serum or plasma chemistry: all calcium, chloride, creatinine, g available), total protein and uri	oumin, alkaline pl lucose, lactate del	nosphatase, alanine transa	minase (ALT)	aspartate aminot	ransferase (AST),	bicarbonate, blood			
d	Hepatitis serology must include recorded in the database. Addit					itis serology is col	llected per institution	onal guidelines, it	should be	
e	COVID-19 infection must be curine, stool, or other bodily fluit testing again.									
f	CCI									
g	Flow cytometry testing of perip	oheral blood will i	nclude, but is not limited	to, CD3+, CD4	4+, CD8+, CD14-	+, CD19+, and CI	D16+/56+ cells.			
h	If a subject is discharged prior	to Day 7, he/she n	needs to visit the site for a	an assessment 2	to 4 days after di	ischarge. Assessm	ents should match	those for Day 10.		
i	Telemedicine is recommended provided the results are ultimat				d survival. Safety	aboratory tests of	can be done at the h	ospital or a local	laboratory	
j	All subjects will be followed for									
k	After signing the ICF, but prior									
1	Screening can be performed wi during this screening window.	thin 1 to 3 days p	rior to dosing, depending	on the local re	quirements for lal	boratory turn-arou	ind times; ECG can	be collected at an	ny time	
m	Serum ferritin, fibrinogen, PT,									
n	Arterial gases should be collect All available data from the arte									
0	CCI	- C						*		
р	For all central laboratory assess	sments, sample co	llection windows of ± 1	day will be allo	wed for each of I	Days 3 and 7.				
q	Per standard of care, chest imaging can be done by chest x-ray or CT scan with contrast, or any other appropriate means to confirm pneumonia prior to or upon hospitalization (within 7 days of randomization).									
r	During screening, vital signs sh closest to randomization should	ould be collected		ndomization of	n Day 1. If more t	han one value is o	obtained for vital sig	gns during screen	ing, the value	

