8.3 On-study Procedures

Planned time points for all on-study procedures are provided in the SoA (Section 1.1). While the subject remains hospitalized, assessments should be performed per SoA until discharge. The date of admission and discharge will be collected for all subjects. If a subject is discharged prior to Day 10, the subject should continue to take acalabrutinib at home. If the subject was discharged prior to Day 7, the subject should return to the clinic 2 to 4 days after discharge and complete the Day 10 assessment as outlined in the SoA.

The following laboratory evaluations will be done at the local laboratories while on study:

- Urine or serum pregnancy test (women of childbearing potential only)
- Hematology studies must include complete blood count (CBC) with differential including, but not limited to white blood cell count, hemoglobin, platelet count, ANC or percentage, red blood cell count, absolute monocyte count or percentage, and absolute lymphocyte count (ALC) or percentage.
- Chemistry will include albumin, alkaline phosphatase, ALT, AST, bicarbonate, BUN, calcium, chloride, creatinine, glucose, LDH, magnesium, phosphate/phosphorus, potassium, sodium, total bilirubin (direct and indirect bilirubin, if available), total protein, and uric acid.

- Arterial blood gases (if available; see Section 8.4.1)
- CRP
- Serum ferritin, fibrinogen, D-dimer, procalcitonin*
- PT, aPTT, INR*
- Cardiac troponin I*
- Hepatitis B serology will be collected as clinically indicated for subjects with a known history of hepatitis B exposure (see Section 6.6.3)

*These laboratory tests should be performed more frequently than described in the SoA (Section 1.1) if clinically indicated.

Samples (peripheral blood samples for mononuclear cells, serum/plasma, and RNA) will be collected per the timepoints delineated in the SoA (Section 1.1) and sent to respective central laboratories for the following tests:

- CCI
- Immunophenotyping: Flow cytometry testing of peripheral blood will include, but is not limited to, CD3+, CD4+, CD8+, CD14+, CD19+ and CD16+/56+ cells
- Serum and nasal swab samples for SARS-CoV-2 viral load/viral shedding
- CCI
- Plasma samples for acalabrutinib/ACP-5862 PK (subjects on acalabrutinib arm only)
- CCI

NOTE: Safety, CRP, PK, PD, and correlative laboratory tests are considered Tier 1 and should not be missed. The site must follow the SoA.

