3.1.15 Relative change from baseline in oxygenation index

This is defined as the percentage change from baseline in oxygenation index (SpO_2/FiO_2) to Days 3, 5, 7 and 10. For this endpoint, baseline is defined as the observation on the date of randomization (Day 1) only.

Oxygenation index is calculated as

$$SpO_2 [\%] / FiO_2 [\text{decimal}]$$

It will be calculated for the baseline and each post-baseline assessment using the SpO_2 (oxygen saturation) value and the FiO_2 (fraction of inspired oxygen) value collected or derived on the VS and OXYGEN or VENTUSE eCRF pages, respectively. Details on these variables and visit windows are provided in Section 3.2.6 and Section 4.1, respectively.

3.1.16 Time to clinical improvement of at least 2 points (from randomization) on a 9-point category ordinal scale through Day 28

This is defined as the time (in days) from randomization to the date of first demonstrated clinical improvement of at least 2 points (i.e., a decline of two points) on the following 9-point category ordinal scale through Day 28:

0. * Uninfected, no clinical or virological evidence of infection
1. Ambulatory, no limitation of activities
2. Ambulatory, limitation of activities
3. Hospitalized – mild disease, no oxygen therapy
4. Hospitalized – mild disease, oxygen by mask or nasal prongs
5. Hospitalized – severe disease, non-invasive ventilation or high flow oxygen
6. Hospitalised – severe disease, intubation and mechanical ventilation
7. Hospitalized – severe disease, ventilation and additional organ support, such as pressors, renal replacement therapy, extracorporeal membrane oxygenation
8. Death

*Score of zero on 9-point category ordinal scale will not be evaluated in this study.

This information will be collected in the OSCI pages in the eCRF as per the SoA in the CSP.

Baseline ordinal scale score is defined as the result obtained on the date of randomization (Day 1) only.

If a subject does not have an event (i.e., does not demonstrate clinical improvement of at least 2 points) on or before Day 28 and does not withdraw or become lost to follow up from the study on or prior to Day 28, the data will be censored at Day 28. If a subject does not have an event but withdraws from the study or is lost to follow up on or prior to Day 28, the data will be censored at the last date known that the subject has not demonstrated clinical improvement of at least 2 points up to Day 28.

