- Baseline is defined as the result obtained on the day of randomization (Day 1) only. Applies to:
 - Respiratory failure status at baseline
 - Baseline oxygen saturation (SpO₂)
 - Baseline for all oxygen and mechanical ventilation assessments
 - Baseline ordinal scale score
 - Baseline mSOFA score
- For all summaries, change from baseline variables will be calculated as the post-baseline value minus the value at baseline. The percentage change from baseline will be calculated as $((\text{post-baseline value} - \text{baseline value}) / \text{baseline value}) \times 100$.
- Unless stated otherwise, visit windows will apply as follows:
 - Day 1 (date of randomization): No window unless specified above (where latest result prior to date of randomization can be used)
 - Days 2-10 or discharge (whichever occurs first): no visit window. Note: if a subject is discharged prior to Day 7 they will visit the site for an assessment 2 to 4 days after discharge. Assessments should match those for Day 10.

- Day 14: ± 2 days
- Day 28: ± 3 days
- Arm 1 Safety follow-up at 28 days after last dose of acalabrutinib: ± 3 days
- Arm 2 Safety follow-up (for AEs, concomitant medications and survival assessment) at 38 days after randomization: ± 3 days
- Long-term follow-up 90 days after randomization: ± 7 days
- Observations recorded on the date closest to the scheduled assessment day (as long as this is within the visit window) will be used as the scheduled assessment. If Any observations recorded outside of the visit window will be considered unscheduled visit observations and will not be included in visit-based summaries at a treatment-group level. If multiple observations are recorded per day, or observations within a visit window are equidistant from the target day, the worst assessment reported will be used as the scheduled assessment. For laboratory and vital signs assessments, this is the maximum reported value.
- Visit-based summaries will include: Baseline (Day 1), Day 2-10, Day 14 and Day 28 where applicable, as per SoA.
- For listings at a subject level, all values will be included (regardless of whether they appear in a corresponding visit-based summary) when deriving a patient level statistic such as a maximum.

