No imputation of values for missing data will be performed except for missing or partial start and end dates for AEs and concomitant medication(CM) (Table 6). If the data cut-off/snapshot date or the subject’s date of death is prior to the date imputed based on the rules outlined below, then the earliest of these dates will be imputed.

Table 6 Imputation rules for missing or partial AE on concomitant medication dates

Form		Imputation	
		Acalabrutinib + BSC	BSC alone
	Start date		
	Missing		

AE and CM	AE/CM ended before first dose date/ randomization date	Impute 1 st January with year being the same year as CM/AE end date	
	AE/CM ended after first dose date/ randomization date	Impute date of first dose	Impute date of randomization
	Partial		
AE and CM	Missing day	Impute 1 st of the month unless AE/CM start month is the same month as the first dose, then impute date of first dose. Check start date is prior to end date.	Impute 1 st of the month unless AE/CM start month is the same month as randomization, then impute date of randomization. Check start date is prior to end date.
	Missing day and month	Impute 1 st January unless AE/CM start year is the same year as the first dose, then impute date of first dose. Check start date is prior to end date. If end date is now prior to start date, impute 1 st January as the start day and month.	Impute 1 st January unless AE/CM start year is the same year as randomization, then impute date of randomization. Check start date is prior to end date. If end date is now prior to start date, impute 1 st January as the start day and month.
	End date		
	Missing		
AE and CM	CM flag ongoing takes any value (yes, no or missing) and CM start date is prior, on or after first dose date/ randomization AE stop date missing	Impute min (date of death, data cut-off/snapshot date)	
	Partial		
CM	Missing day	Impute the last day of the month unless month is the same as month of last dose, then impute date of last dose.	Impute the last day of the month unless month is the same as month of randomization date + 10 days, then impute randomization date + 10 days.

	Missing day and month	Impute date of last dose + 28 days + 3 days	Impute date of randomization + 38 days + 3 days
--	-----------------------	---	---

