4.3.2.14 Relative change from baseline in oxygenation index

Summary statistics (n, mean, median, SD, minimum, and maximum) and the percent change from baseline to each scheduled study assessment will be presented by treatment group.

Box plots of absolute value over time and a line graph of mean change (and SD) from baseline to each scheduled study assessment may be presented for each treatment group.

A by-subject listing will also be presented.

4.3.2.15 Time to clinical improvement of at least 2 points (from randomization) on a 9-point category ordinal scale through Day 28

Time from randomization to the date of first demonstrated clinical improvement of at least 2 points on a 9-point category ordinal scale through Day 28 will be portrayed using the KM method by treatment group.

Alongside summary statistics, a KM plot of the cumulative improvement rate over time will be presented by treatment group.

The HR and its 90% CI will be estimated from a stratified Cox Proportional Hazards model (with ties = Efron), stratified by age (<65 vs ≥65 years) and comorbidities (present vs absent).

The CI will be calculated using a profile likelihood approach. Summary statistics will include the lower and upper quartile and median time to clinical improvement with the 90% CI.

The method for handling subjects that withdraw or are lost to follow up or die is detailed in Section 3.1.16.

In addition to the above, for each treatment group, ordinal scale scores will be presented by day and the change in the score from baseline to each post-baseline assessment will be summarized.

Additional sensitivity analyses may be performed as appropriate.

Time to clinical improvement of at least 2 points (from randomization) on a 9-point category ordinal scale, live discharge from hospital, or considered fit for discharge, whichever comes first) through

Time from randomization to the date of first demonstrated clinical improvement of at least 2 points on a 9-point category ordinal scale, live discharge from hospital, or considered fit for discharge, whichever comes first, through Day 28 will be portrayed using the KM method by treatment group.

Alongside summary statistics, a KM plot of the cumulative improvement rate over time will be presented by treatment group.

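### The Day 2-10 change-from-baseline summary of the 9-point scale covers only subjects still in hospital, so it understates improvement, more so in the arm that discharges faster

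*Protocol*

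**What the plan says.** **Collection.** In Tables 1 and 2 of Protocol 1.1, the row "9-point ordinal scale" is marked at screening, in the column "Daily until hospital discharge", and at Days 14 and 28. It is blank under Day 10 or discharge. Protocol 8.3 adds: "While the subject remains hospitalized, assessments should be performed per SoA until discharge". A subject discharged before Day 7 returns 2 to 4 days later, but for that visit "Assessments should match those for Day 10", and the Day 10 column has no scale mark. SAP 3.1.16 adds no other source: "This information will be collected in the OSCI pages in the eCRF as per the SoA in the CSP".

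**Analysis.** SAP 4.3.2.15 states, after the Kaplan-Meier and Cox analysis, that "ordinal scale scores will be presented by day and the change in the score from baseline to each post-baseline assessment will be summarized". SAP 4.1 fixes the days: "Visit-based summaries will include: Baseline (Day 1), Day 2-10, Day 14 and Day 28 where applicable". It also states: "No imputation of values for missing data will be performed except for missing or partial start and end dates for AEs", with concomitant medication dates as the only other exception. Under the same section, continuous summaries use non-missing observations. Categorical summaries show a missing count, with percentages on the arm total unless stated otherwise.

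**Discharge and death.** No rule gives a score to a discharged subject between discharge and Day 14. Death is category 8 on the scale, but neither document says whether 8 is entered again on later days.

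**The concern.** Presence in the Day 2-10 change summary depends on the outcome being measured. A subject who goes home on Day 6 has no score on Days 7 to 10 and so leaves the summary because of recovery. Those who remain are the sicker part of the arm. The faster an arm discharges, the more its best results are missing, so the comparison between arms is distorted as well as the level within each arm.

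The frequency tables have a different weakness. Their percentages are not inflated, but the missing row combines subjects who have gone home with those lost to follow-up. If 8 is not repeated after death, it also holds the deaths. The best and worst outcomes then share one line.

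At stake is the reading of a descriptive trajectory that the SAP amendment history says was added to help interpretation. A reader could take it as slower recovery, or even deterioration, in an arm that is doing well.

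**Working it through.** The documents give no figure on this point, so there is nothing to reproduce. All distributions below are assumed. Every subject starts at score 4. Discharged subjects are given 2 and dead subjects 8.

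**General relation.** Let d be the proportion discharged, m the proportion dead, and h the mean score of those in hospital.

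- All-subject mean = 2d + 8m + (1 - d - m)h
- In-hospital mean = h
- In-hospital minus all-subject = d(h - 2) - m(8 - h)

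The first term grows with discharge and hides improvement. The second arises only if deaths carry no score, and works the other way. At h = 4.5 the difference is 2.5d - 3.5m, so improvement is understated whenever d exceeds 1.4m. If deaths are kept as 8, only the low scores are removed and improvement is always understated.

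**Example A, Day 10** (5.5 stands for a mix of scores 5 and 6)

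| Arm | Home (2) | Score 4 | Score 5.5 | Dead (8) |
|---|---|---|---|---|
| BSC | 50% | 25% | 15% | 10% |
| Acalabrutinib | 70% | 20% | 5% | 5% |

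- All subjects, BSC: 1.00 + 1.00 + 0.825 + 0.80 - 4 = -0.375.
- All subjects, acalabrutinib: 1.40 + 0.80 + 0.275 + 0.40 - 4 = -1.125. Difference -0.75.
- In hospital, BSC: (1.00 + 0.825)/0.40 - 4 = +0.56.
- In hospital, acalabrutinib: (0.80 + 0.275)/0.25 - 4 = +0.30. Difference -0.26, so about 65% of the effect is lost.
- Discharged omitted but deaths kept as 8: 2.625/0.50 - 4 = +1.25 and 1.475/0.30 - 4 = +0.92. Difference -0.33.

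**Example B, Day 10**, same columns: BSC 50/30/15/5%, acalabrutinib 75/12/10/3%.

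- All subjects: 3.425 - 4 = -0.575 and 2.77 - 4 = -1.23. Difference -0.655.
- In hospital: 2.025/0.45 - 4 = +0.50 and 1.03/0.22 - 4 = +0.68. Difference +0.18, which is reversed.
- Deaths kept as 8: 2.425/0.50 - 4 = +0.85 and 1.27/0.25 - 4 = +1.08. Difference +0.23, still reversed.

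**Example C, whole scores, one arm of 30** (the planned arm size) at Day 10: 21 discharged, 8 in hospital (one at 3, two at 4, two at 5, three at 6), 1 dead.

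- In hospital: 39/8 - 4 = +0.88.
- With the death as 8: 47/9 - 4 = +1.22.
- All 30: (42 + 39 + 8)/30 - 4 = -1.03.
- Share at score 5 or 6 in a frequency table: 5/30 = 17% on the arm total, against 5/8 = 62% on those observed. The SAP default gives the 17%.

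**Range of conditions.** A simulation moved subjects at most one point a day over Days 2 to 10. At scores 3-4 the daily probability of improving was 0.15 to 0.45 and of worsening 0.03 or 0.05. At 5 and above these were 0.08 and 0.06. Score 2 counted as discharged. Across seven combinations, the Day 10 mean change ran from -0.27 to +0.43 in hospital and from -0.88 to -1.79 over all subjects. Improvement was understated in all seven. The sign turned positive in three (+0.14, +0.21, +0.43), with 23%, 10% and 13% still in hospital. A fourth, with 19% in hospital, stayed negative at -0.11.

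**The case against.** The strongest reply is that this is a supplementary table with no test attached. The secondary endpoint is the time-to-event analysis, and other SAP outputs deal with discharge and death directly: time to improvement or live discharge, time to recovery, days hospitalized, days alive outside hospital, and Day 90 mortality. This stands as a limit on importance. It does not make the table correct. It also shows that the SAP states such rules elsewhere, including an imputed FiO2 of 21% in SAP 3.2.6 when no oxygen is reported.

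Second, SAP 4.3.2.15 says only that change is summarised and names no mean. If change were tabulated by category, the arm-total denominator would apply. This stands in part: the figures above concern a mean change under the continuous-variable rule of SAP 4.1. The merged missing row would remain in either case.

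Third, the illustrations can be made to give the result wanted. Examples A and B put nobody in hospital at score 3 and everyone at baseline 4, so the in-hospital mean cannot fall below baseline. They also leave out eligible subjects with respiratory failure at baseline, who can improve while in hospital. This is fair as to sign. Example C and the simulation allow score 3 and still show understated improvement, but they show false worsening only sometimes.

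A reader might also infer that the by-day tables drop deaths. The documents do not say so. Category 8 exists, Days 14 and 28 are scheduled without a hospital condition, and handling after death is simply not stated.

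**Conclusion.** The point holds for the Day 2-10 change-from-baseline summary. Followed as written, it describes only subjects still in hospital and understates improvement, with a larger distortion in an arm that discharges faster. In Example A the arm difference shrinks from -0.75 to -0.26; in Example B, -0.655 becomes +0.18. These sizes rest on assumed distributions and on change being summarised as a mean. If deaths also carry no score, the direction further requires discharges to outweigh deaths as shown above.

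Three stronger readings are not supported. False worsening or reversed arms are possible but not general. Severe-category percentages in the frequency tables are not inflated, because the denominator is the arm total. The discharge gap does not extend to Days 14 and 28, where discharged subjects are scheduled for scoring; only the unstated handling of death remains open there.

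The primary endpoint and the time-to-improvement analysis do not draw on these tables and are not affected. This is a modest correction to a descriptive output.

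**What to change.** In SAP 4.3.2.15, add an exception to the no-imputation rule of SAP 4.1, limited to the by-day and change-from-baseline ordinal tables:

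- (a) Carry score 8 forward on every day from the date of death.
- (b) From discharge until the next recorded score, show living discharged subjects in a separate category, labelled as discharged with a score of 2 or less, and use 2 for the change score.
- (c) Apply the change summary to all randomized subjects with known status, and keep the missing row for withdrawn or lost subjects only. The frequency tables already use the arm total, so there the gain is in separating discharged, dead and lost subjects.

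The cost is a few lines of SAP text and programming. Discharge and death dates are already collected, so no new data are needed. The one small downside is that a discharged subject whose true score is 1 is counted as 2 until the next visit.
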